6.4. Adverse Event Management

The Investigator (or designee) will provide appropriate medical care for the clinical management of any AEs related to study participation, whether identified during or after the course of study participation. Evaluation and treatment of any AE (or CS laboratory abnormality) is at the discretion of the Investigator based on their clinical judgment. The applied measures should be recorded in the patient's source documents and entered in the eCRF as applicable. Referral or collaborative care will be organized if considered necessary by the Investigator. As noted in

Section 6.7, the Sponsor may request additional supplemental investigations as needed to elucidate the nature and/or causality of an SAE.

Serious AEs will be reported to competent authorities in accordance with national requirements.

6.5. Recording of Adverse Events and Serious Adverse Events

When an AE/SAE occurs, it is the responsibility of the Investigator (or designee) to review all documentation (e.g., hospital progress notes, laboratory results, patient diaries, and diagnostics reports) relative to the event. The Investigator (or designee) will then record all relevant information regarding an AE/SAE in the eCRF. It is not acceptable for the Investigator (or designee) to send photocopies of the patient's medical records to the Sponsor in lieu of completion of the appropriate AE/SAE eCRF pages. However, there may be instances when the Sponsor requests copies of medical records for certain cases. In this instance, all patient identifiers will be blinded on the copies of the medical records before submission to the Sponsor.

The Investigator (or designee) will attempt to establish a diagnosis of the event based on signs, symptoms, and/or other clinical information. In such cases, the diagnosis should be documented as the AE/SAE and not the individual signs/symptoms.

6.6. Serious Adverse Event Reporting

6.6.1. Regulatory Reporting Requirements for Reporting of Serious Adverse Events

The Investigator (or designee) will promptly report all SAEs to the Sponsor (or delegate). Prompt notification of SAEs by the Investigator (or designee) to the appropriate Sponsor (or delegate) contact for SAE receipt **is essential** so that the Sponsor may comply with its regulatory obligations. Serious AEs will be reported to regulatory authorities in accordance with national requirements.

The Sponsor is responsible for notifying the local regulatory authorities of all SAEs that occur at the site. It is the Sponsor's responsibility to report all SUSARs promptly.

The Principal Investigator (or designee) is responsible for notifying the local institutional review board (IRB) or the relevant local regulatory authority of all SAEs that occur at his or her site as required.

6.6.2. Completion and Transmission of the Serious Adverse Event Reports

Once the Investigator (or designee) becomes aware that an SAE has occurred in a study patient, he/she will report the information to the Sponsor (or delegate) and the Sponsor's Medical Monitor within 24 h. The SAE form/eCRF will always be completed as thoroughly as possible with all available details of the event, signed by the Investigator (or designee), and forwarded to the Sponsor (or delegate) and the Sponsor's Medical Monitor within the designated time frames. If the Investigator does not have all information regarding an SAE, he/she will not wait to receive additional information before notifying the Sponsor (or delegate) and the Sponsor's Medical Monitor of the event and completing the form/eCRF. The form/eCRF will be updated as soon as possible when additional information becomes available.

The Investigator will always provide an assessment of causality at the time of the initial report.

Completion of the SAE form/eCRF in an electronic data capture (EDC) system is the preferred method to transmit this information to the Sponsor (or delegate) and the Sponsor's Medical Monitor for SAE receipt. In rare circumstances, and in the absence of facsimile, computer and scanner equipment, notification by telephone is acceptable, with a copy of the SAE form sent by overnight mail. Initial notification via the telephone does not replace the need for the Investigator (or designee) to complete and sign the SAE form/eCRF within the outlined time frames.

Any event that in the opinion of the Investigator (or designee) may be of immediate or potential concern for the patient's health or well-being will be reported to the Sponsor's Medical Representative or emergency contact.

Adverse events will be classified as SUSARs if the AE or suspected adverse reaction meets the definition of "unexpected" in [Section 6.1](#). All SUSARs should be reported to the ethics committee and regulatory authority in accordance with applicable regulatory requirements for expedited reporting. It is the Sponsor's responsibility to report SUSARs to the ethics committee and regulatory authority.

6.6.3. Post-study Adverse Events and Serious Adverse Events

A post-study AE/SAE is defined as any event that occurs outside of the nominal AE/SAE study detection period.

Investigators are not obligated to actively seek AE/SAE information in former study patients. However, if the Investigator (or designee) learns of any SAE, including a death, at any time after a patient has completed the study and he/she considers the event reasonably related to the study drug, the Investigator will promptly notify the Sponsor.

6.7. Follow-up of Adverse Events and Serious Adverse Events

After the initial AE/SAE report, the Investigator (or designee) is required to proactively follow each patient and provide further information to the Sponsor on the patient's condition.

All AEs and SAEs documented at a previous visit/contact and are designated as ongoing will be reviewed at subsequent visits/contacts. All AEs must be followed until the patient has recovered/resolved and all queries have been resolved, or until deemed medically stable by the Investigator (or designee). For cases of chronic conditions or if the patient dies from another event, follow-up until the outcome category is "recovered/resolved" is not required, as these cases can be closed with an outcome of "recovering/resolving" or "not recovered/not resolved."

All patients with SAEs will be followed until they have recovered/resolved, recovered/resolved with sequelae, or the event was fatal, or until all queries have been resolved or the patient is lost to follow-up. Once resolved, the appropriate SAE report will be updated. The Investigator will ensure that follow-up includes any supplemental investigations as may be indicated to elucidate the nature and/or causality of the SAE. This may include additional laboratory tests or investigations, histopathological examinations, or consultation with other health care professionals.

The Sponsor may request that the Investigator perform or arrange for the conduct of supplemental measurements and/or evaluations to elucidate as fully as possible the nature and/or causality of the SAE. If a patient dies during participation in the study or during a recognized

follow-up period, the Sponsor will be provided with a copy of any postmortem findings, including histopathology.

New or updated information will be recorded on the originally completed SAE form and the eCRF, with all changes signed and dated by the Investigator. The Sponsor should be notified of the updated SAE form/eCRF.

6.8. Clinical Laboratory Evaluations

A change in the value of a clinical laboratory assessment can represent an AE if the change is clinically relevant or if, during treatment with the study drug, a shift of a parameter is observed from a normal value to an abnormal value, or a further worsening of an already abnormal value. When evaluating such changes, the extent of deviation from the reference range, the duration until return to the reference range, either while continuing treatment or after the treatment with study drug, and the range of variation of the respective parameter within its reference range, must be taken into consideration.

The Investigator should decide, based on the above criteria and the clinical condition of a patient, whether a change in a clinical laboratory parameter is CS and therefore represents an AE.

6.9. Pregnancy

Any report of pregnancy for any female study patient or male study patient's partner must be reported within 1 business day to the Sponsor (or designee) and the Sponsor's Medical Monitor. The female study patient must be withdrawn from the treatment.

A serum pregnancy test will be performed on all women of childbearing potential.

Every effort should be made to gather information regarding the pregnancy outcome and condition of the infant. It is the responsibility of the Investigator to obtain this information within 30 calendar days after the initial notification and approximately 30-calendar days postpartum.

Pregnancy complications such as spontaneous abortion/miscarriage or congenital abnormality are considered SAEs and must be reported to the Sponsor (or designee) and the Sponsor's Medical Monitor.

Pregnancy outcomes should be collected for female partners of any males who took the study drug if possible. Consent to report information regarding these pregnancy outcomes should be obtained from the mother.

Note: An elective abortion is not considered an SAE.

In addition to the above, if the Investigator determines that the pregnancy meets serious criteria, it must be reported as an SAE. The test date of the first positive serum/urine β -human chorionic gonadotropin test or ultrasound result will determine the pregnancy onset date.

6.10. Abuse, Misuse, Overdose, and Medication Error

Abuse, misuse, overdose, or medication error (as defined below) must be reported to the Sponsor according to the SAE reporting procedure whether or not they result in an AE/SAE. *Note:* The 1-business-day requirement for reporting SAEs does not apply to reports of abuse, misuse, overdose, or medication errors unless these result in an SAE.

The categories below are not mutually exclusive; the event can meet more than 1 category.

- **Abuse:** Persistent or sporadic intentional intake of study drug when used for a nonmedical purpose (e.g., to alter one's state of consciousness or get high) in a manner that may be detrimental to the individual and/or society
- **Medication Error:** An error made in prescribing, dispensing, administration, and/or use of a study drug (for studies, medication errors are reportable to the Sponsor)
- **Misuse:** Intentional use of study drug other than as directed or indicated at any dose (*Note:* this includes a situation where the study drug is not used as directed at the dose prescribed by the protocol)
- **Overdose:** Intentional or unintentional intake of a dose of a study drug exceeding a prespecified total daily dose of the product

Cases of patients missing doses of product are not considered reportable as medication errors.

Medication errors should be collected/reported for all products under investigation.

The administration and/or use of the unassigned treatment is always reportable as a medication error. The administration and/or use of an expired product should be considered as a reportable medication error.

Errors related to administration of study drug are reportable as medication errors.

Intentional overdosing of study drug is unlikely. In the event of overdose in general, treatment should be supportive and symptomatic according the patient's clinical presentation.

6.11. Reference Safety Information

The reference for safety information for this study is the IB, which the Sponsor has provided separately to all Investigators.

The reference for safety information for the comparator in this study are Summary of Product Characteristics/Product Package Inserts.

7. DATA MANAGEMENT

7.1. Data Management Considerations

Electronic case report forms will be employed for this study. Completed eCRFs for this study will be forwarded to the Sponsor or its representative where editing and construction of a quality-assured database will occur. Data will be quality checked and electronically verified after entry into the database. Queries will be issued for any inconsistencies, omissions, and discrepancies and will be resolved by the appropriate parties. The statistical analysis of these data will be performed by the Sponsor or its representative. All AEs will be coded using the Medical Dictionary for Regulated Activities (MedDRA). Concomitant medications will be coded using WHODrug Global. Data management details will be outlined in a separate data management plan.

8. STATISTICAL CONSIDERATIONS

The statistical analysis will be undertaken by Synteract in collaboration with Spero.

A detailed statistical analysis plan (SAP) will be finalized and signed before database lock and before analysis of the study being carried out. Any deviations from the analyses described below will be included in the clinical study report.

Continuous variables will be summarized with means, standard deviations, medians, minimums, and maximums. Other summaries (e.g., quartiles, confidence intervals) may be used as appropriate.

Categorical variables will be summarized by frequency and by percentage of patients in corresponding categories.

All summary tables will be presented by treatment arm. Disposition, demographic, and baseline summaries will also include a total summary column. All data reported for a patient during the study and all derived data will be presented in data listings.

8.1. Endpoints

8.1.1. Primary

- Maximum plasma concentration (C_{max}), time to reach C_{max} (T_{max}), area under the concentration-time curve from zero to τ , where τ is the dosing interval ($AUC_{0-\tau}$), and accumulation ratio of SPR719 on Day 1 and Day 28

8.1.2. Secondary

- Reported AEs
- Clinically meaningful change in physical examination findings
- Concomitant medication usage
- Changes from baseline in laboratory tests
- Clinically significant out-of-normal range laboratory tests
- Shifts from baseline for selected laboratory tests using National Cancer Institute CTCAE v5.0 shift categories
- Changes from baseline in vital sign measurements (body temperature, heart rate, respiratory rate, blood pressure)
- 12-lead ECGs

[REDACTED]

- | [REDACTED]
- | [REDACTED]
- | [REDACTED]
- | [REDACTED]
- | [REDACTED]
- | [REDACTED]
- | [REDACTED]
- | [REDACTED]
- | [REDACTED]

[REDACTED]

8.1.4. Determination of Sample Size

This study will be conducted to evaluate the PK and safety of SPR720 in a patient population with NTM-PD and to evaluate the efficacy of SPR720 compared with placebo in patients with NTM-PD.

There is no formal statistical hypothesis planned, and the sample size is mainly based on an estimated number of patients needed to understand the PK and safety of patients in this study.

8.1.5. Analysis Populations

Safety Analysis Population:

The Safety Population will include all randomized patients who received any amount of IP. Patients will be summarized by the treatment which they received.

[REDACTED]

**Pharmacokinetic Analysis Population:**

The PK Population will include all patients treated with at least 1 dose of SPR720 and who have at least 1 analyzable plasma PK sample.

8.1.6. Protocol Deviations

Protocol deviations will be assessed and documented on a case-by-case basis while blinded to treatment arm. Protocol deviations, including the deviation designation (major or minor) and deviation category will be presented in a data listing.

8.1.7. Demographic and Baseline Characteristics

Patient disposition, demographics, and baseline characteristics will be summarized using descriptive statistics for the Safety and micro-ITT Populations. No formal statistical analysis tests will be performed.

8.1.8. Pharmacokinetic Analyses

Dates and times of blood samples as well as dates and times of study drug administration will be recorded. Plasma concentration-time data from intensive PK sampling patients will be subjected to noncompartmental PK analysis. Day 1 and Day 28 PK parameters including, but not limited to, C_{max} , T_{max} , area under the concentration-time curve from zero to last concentration (AUC_{last}), $AUC_{0-\tau}$, accumulation ratio, and plasma concentration at the end of a dosing interval at steady state (taken directly before next administration) (C_{trough}) will be determined when appropriate for SPR719. Concentration data from sparse sampling will be compiled for summary statistics of C_{trough} across various days. Concentration data from SPR720 recipients will be used for the development of a PK Population model, for PK analysis, and for estimation of individual PK profiles in patients with sparse sampling, which will be reported in a separate report.

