Statistical Methods:	
Presentation of PK and safety data will be produced for the PK Population and Safety Population, respectively.
 
A PK Population model will be developed using data from the completed Phase 1 study of single-ascending/multiple-ascending doses in normal healthy volunteers (Study SPR720-101). This population model will be used to estimate PK parameters for patients in the SPR720-201 study.
 
Dates and times of blood samples as well as dates and times of study drug administration will be recorded. Plasma concentration-time data from intensive PK sampling patients will be subjected to noncompartmental PK analysis. Day 1 and Day 28 PK parameters including, but not limited to, C_{max}, T_{max}, area under the concentration-time curve from zero to last concentration (AUC_{last}), AUC_{0-t}, accumulation ratio, and plasma concentration at the end of a dosing interval at steady state (taken directly before next administration) (C_{trough}) will be determined for SPR719. Concentration data from sparse sampling will be compiled for summary statistics of C_{trough} across various days. Concentration data from SPR720 recipients will be used for the development of a PK Population model, for PK analysis, and for estimation of individual PK profiles in patients with sparse sampling, which will be reported in a separate report.
 
Patient disposition, demographics and baseline characteristics, IP exposure, and prior and concomitant medications will be summarized.
 
All safety presentations will be descriptive, and all summaries will be displayed by treatment arm. Summary statistics for continuous variables will include the sample size, mean, standard deviation, minimum, median, and maximum. For categorical data, summaries will include the frequency and percentage. The incidence and frequency of AEs and serious AEs will be summarized by treatment arm by severity and relationship. Laboratory results will be summarized by treatment arm for each time point and change from baseline at each postbaseline time point. Frequency and percentage for laboratory tests that are considered CS and out of range will be presented. In addition, shifts from baseline using CTCAE v5.0 by treatment arm for selected laboratory tests (aspartate aminotransferase, alanine aminotransferase, gamma-glutamyltransferase, alkaline phosphatase, total bilirubin, amylase, lipase, blood urea nitrogen, serum creatinine, creatinine clearance, hemoglobin, hematocrit, neutrophils, lymphocytes, and erythrocytes) will be presented. Vital signs and 12-lead ECG parameters will be summarized and will include change from baseline. Twelve-lead ECGs including QTc intervals will also be summarized as clinically meaningful changes in physical examination findings.
  

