- e. Height required only at screening. Body weight (kg) will be measured at screening and on Days 1, 7, 14, 21, and 28.
- f. Full physical examinations will include the following (at a minimum): skin, head, ears, eyes, nose and throat, respiratory system, cardiovascular system, gastrointestinal system, neurological condition, blood and lymphatic systems, and the musculoskeletal system. Symptom-directed physical examinations will be conducted at study visits on Days 7, 14, 21, and 28.
- g. Vital signs will include systolic and diastolic blood pressure, pulse, temperature, and respiratory rate. Vital sign measurements should be assessed 1 h post-dose (± 15 min). For patients randomized to Treatment Arm 4 (SOC), vital sign measurements can be performed at any time.
- h. On Days 1, 14, and 28, perform the ECG at 1 h post-dose (± 15 min). For patients randomized to Treatment Arm 4 (SOC), ECG can be performed at any time.
- i. A serum pregnancy test will be performed on all women of childbearing potential at screening and Day 1, and, for patients in Treatment Arms 1, 2, and 3, at the follow-up visit 28 days after EOT. On Day 1, serum pregnancy should be confirmed pre-dose.
- j. Microscopic urinalysis will be performed.
- k. Refer to Table 3 for the list of serum chemistry, hematology, coagulation, and calculated creatinine clearance assessments.
- l. Intense PK sampling will take place at selected sites only. On Days 1 and 28: pre-dose (no greater than 1 h prior to dose), post-dose at 1 h (± 5 min), 2 h (± 10 min), 4 h (± 10 min), 8 h (± 15 min), 12 h (± 30 min), and 24 h (± 1 h, but -15 min prior to the next daily dose). On Days 7, 14, and 21: pre-dose (± 1 h) (no greater than 1 h prior to dose), 1 h post-dose (± 30 min), and just before discharge from clinic or at minimum 3 hours post-dose.
- m. Sparse PK sampling will take place at remaining sites. On Days 1, 7, 14, 21, and 28: pre-dose (no greater than 1 h prior to dose), 1 h post-dose (± 30 min), and just before discharge from the clinic or at minimum 3 hours post-dose.
- n. Serum samples for biomarker assessment using the Nanodisk-MS assay will be collected on Days 1, 7, 14, 21 and 28. Biomarker assay will be nanotechnique quantitative detection of NTM specific peptides in serum.

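### Does the plan leave open whether the primary PK endpoints are noncompartmental or model-based?

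*Combined protocol and SAP*

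**What the plan says.** Section 8.1.1 lists the primary endpoints as Cmax, Tmax, AUC0-τ and "accumulation ratio of SPR719 on Day 1 and Day 28". It gives no estimation method and no patient set.

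Section 8.1.8 supplies the method: "Plasma concentration-time data from intensive PK sampling patients will be subjected to noncompartmental PK analysis". The next sentence lists the Day 1 and Day 28 parameters, to be determined where appropriate. Sparse data are then used for trough summaries. The section closes with the model: "Concentration data from SPR720 recipients will be used for the development of a PK Population model, for PK analysis". That closing sentence also covers the individual profiles of sparsely sampled patients, which go to a separate report.

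The synopsis (Statistical Methods) repeats most of this but adds three statements. On analysis sets it says that "Presentation of PK and safety data will be produced for the PK Population and Safety Population, respectively". On the origin of the model, the wording is that "A PK Population model will be developed using data from the completed Phase 1 study" in healthy volunteers. On its purpose, the synopsis says: "This population model will be used to estimate PK parameters for patients in the SPR720-201 study".

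Section 8.1.5 defines the PK Population as patients given at least one dose of SPR720 "who have at least 1 analyzable plasma PK sample", so it includes intensive and sparse patients alike. Note m to Table 2 says "Sparse PK sampling will take place at remaining sites", with samples pre-dose, at 1 h, and at discharge or no earlier than 3 h after the dose. Section 8 announces a detailed SAP, to be signed before database lock and before the analysis. Its text is not part of the document reviewed here.

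**The concern.** PK in patients is the primary objective, so one expects the plan to say which estimates form the primary result. No sentence does. The only PK analysis set is the all-patient one in section 8.1.5, and it cannot be the denominator for a noncompartmental AUC0-τ, because sparse patients have no scheduled samples over the later part of the dosing interval. Taken alone, the synopsis sentence on the population model could mean that model-based estimates for all SPR720 patients are the result that counts.

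The two readings differ in method and, about fourfold, in patient number. If the choice really were open, a reader could not tell in advance how precise the headline figure would be or whose exposure it described. The synopsis also raises a question about the model itself. If it were built on Phase 1 volunteers and then held fixed, estimates for sparsely sampled patients would be drawn towards healthy-volunteer values.

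**Working it through.** **1. The plan's own patient numbers (section 3.1).** Sparse sites enrol 72 patients at 5:5:5:4; intensive sites enrol 18 at 1:1:1.

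- Arms 1 to 3, sparse: 72 × 5/19 = 18.9 each (plan: 19 to 20).
- Arm 4, sparse: 72 × 4/19 = 15.2 (plan: 15 to 16).
- Check: 3 × 19 + 15 = 72, and 72 + 18 = 90, the planned total.
- PK Population per SPR720 dose: 18.9 + 6 = 24.9, about 25.
- Intensive share per dose: 6/24.9 = 24%.

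The numbers reproduce. Six per dose is the lower bound: the allocation paragraph of section 3.1 gives 6 per arm, while its PK paragraph and section 5.3 give at least 6.

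**2. What the choice would be worth.** For a geometric mean, the 95% interval is the estimate multiplied and divided by exp(t × σ/√n), with t the 0.975 quantile on n − 1 degrees of freedom and σ = √ln(1 + CV²). The documents give no CV, so 30% and 50% are assumed.

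| Assumed CV | σ | n = 6 (t = 2.571) | n = 25 (t = 2.064) |
|---|---|---|---|
| 30% | 0.294 | ×/÷1.36 | ×/÷1.13 |
| 50% | 0.472 | ×/÷1.64 | ×/÷1.22 |

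The n = 25 column treats model-based individual estimates as if they had been observed. It ignores model error and is a best case, so the comparison flatters the model.

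**3. Which source the text assigns to each parameter.**

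| Item | Intensive patients | Sparse patients |
|---|---|---|
| Samples on Days 1 and 28 | Pre-dose, 1, 2, 4, 8, 12, 24 h | Pre-dose, 1 h, discharge or at least 3 h |
| Method in 8.1.8 | Noncompartmental | Trough summary; population model |
| Cmax, Tmax, AUC0-τ, accumulation ratio | Listed directly after the noncompartmental sentence | Only through the model |
| Where reported | No separate report stated | Individual profiles in a separate report |

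The four primary endpoints all appear in the list that follows the noncompartmental sentence. They are set for Days 1 and 28, the only days with full profiles, and only intensive patients have those profiles. The one descriptive use of sparse data, the trough, is not a primary endpoint. Every line of the table points to the noncompartmental reading.

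**4. The PK Population.** Presenting PK data for this set is compatible with summarising each parameter in those members for whom it can be determined. The set is also needed for the trough summaries and the model, so its breadth does not make it a rival primary set.

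**5. The source of the model.** The synopsis starts the model from Phase 1 data. Both the synopsis and section 8.1.8 then put concentrations from SPR720 recipients into its development. A model frozen on healthy volunteers is therefore not what the text describes, and any bias from one is speculative.

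**The case for a change.** The strongest opposing case is that a primary endpoint should not depend on the order of sentences. The endpoint section is silent, the synopsis sentence on the model is not limited to supportive use, and the only defined PK set does not fit a noncompartmental AUC0-τ. In a study without a hypothesis test, the PK estimate is the main deliverable, so both its precision and its meaning depend on the unnamed choice. The announced SAP might settle the matter, but its text cannot be checked here.

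Part of this stands. No passage labels the noncompartmental parameters as primary, and the synopsis is not aligned with section 8.1.8. There is no stated rule for an evaluable profile beyond the words on appropriateness, and the statements of 6 per arm and at least 6 per arm could be worded alike.

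None of it shows that the plan, followed as written, gives a wrong result. The noncompartmental analysis is committed regardless, and the model-based sparse profiles are kept apart by their own report. Section 8.1.4 states that no formal hypothesis is planned, so no error rate, power or decision rule depends on the label. Early withdrawals would thin the Day 28 profiles, since section 3.3.6 rules out replacement, but naming a primary method would not alter that. Evaluability rules and table layout are ordinary SAP content.

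**Conclusion.** The concern does not call for a change. The plan implies, without saying so, that the primary PK results are the noncompartmental parameters in intensively sampled SPR720 patients: at least 6 per dose, out of about 25 per dose in the PK Population. An analyst following section 8.1.8 would reach that reading and report sound results, with the population model as a separate piece of work.

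The difference in precision between the two readings is real: ×/÷1.64 against at best ×/÷1.22 at a CV of 50%, and ×/÷1.36 against at best ×/÷1.13 at 30%. It describes the cost of a small intensive subset; it is not the consequence of an error. The figures rest on assumed CVs, a log-normal distribution, exactly 6 intensive patients per dose, and no model error in the larger set. The conclusion rests on the reading of section 8.1.8, on the study being descriptive, and on the SAP being signed before analysis as section 8 requires. What remains is a matter of labelling that corrects no result.
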